5.11.6. Health Outcomes Analyses

Patients and caregivers who are enrolled at sites in the US and who speak English will be asked to participate in Pediatric Quality of Life (PedsQL) addendum I8B-MC-ITSB(1). The PedsQL Population includes all randomized patients who have an informed consent for the PedsQL addendum signed by parent(s)/legal guardian(s) and completed PedsQL questionnaire at both baseline (Visit 4) and post-baseline (Visit 15 or early discontinuation [ED]). The PedsQL Population will be used for all analyses specified in this section.

Baseline demographics and characteristics of patients participating in the PedsQL addendum will be summarized by treatment. The PedsQL Generic Core and PedsQL 3.2 Diabetes Module will be scored according to the user manuals.

For the PedsQL Generic Core (4.0) (Varni et al. 2003) and PedsQL Diabetes (3.2) (Varni et al. 2013) scales, transformation of scores are needed as indicated by the scoring manual. Items are scored on a 5-point Likert scale from 0 (Never) to 4 (Almost always). Items are then reversed scored as follows: 0=100, 1=75, 2=50, 3=25, 4=0. The dimension scores and the summary scores are calculated by summing the transformed scores of the items divided by the number of items answered. Moreover, for both the PedsQL Generic Core (4.0) and PedsQL Diabetes (3.2) scales, if more than 50% of the items in the scale are missing, then the Scale Scores should not be computed. If 50% or more items are completed, mean of the completed items in a scale will be used to impute the missing scores.

The PedsQL Diabetes (3.2) and PedsQL Generic Core (4.0) scales will be analyzed by ANCOVA model using treatment, strata (pooled country, type of basal insulin, and HbA1c stratum) as fixed effects and baseline score as a covariate. The analyses will cover the total scores, all subscale scores, and dimensions.

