An analysis of covariance (ANCOVA) will also be used to analyze continuous variables. The model for the change from baseline to the Week 26 HbA1c endpoint will include treatment and strata (pooled country, type of basal insulin, and age group) as fixed effects and baseline as a covariate. Unless otherwise stated, missing endpoints will be imputed using the last-observation-carried-forward (LOCF) approach, using only postbaseline data. For analyses of variables other than HbA1c, the HbA1c stratum ( $\leq 8.0\%$ ,  $> 8.0\%$ ) will be included in the model.

For continuous measures, summary statistics will include sample size, mean, SD, median, and minimum and maximum for both the actual and the change from baseline measurements. The LS means and standard errors derived from the analysis models will also be displayed for the change from baseline measurements. Treatment comparisons will be displayed showing the treatment difference LS means and the 95% CIs for the treatment differences along with the p-values for the treatment comparisons.

For categorical measures, summary statistics will include sample size, frequency, and percentages. Fisher's exact test or Pearson's chi-square test will be used for treatment comparisons.

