5.2. Adjustments for Covariates

Stratification factors of this study include country, HbA1c stratum ($\leq 8.0\%$, $>8.0\%$), type of basal insulin at randomization (insulin glargine, detemir or degludec), and age group (1 to <12, 12 to <18 years). Stratification factors will be entered into the interactive web-response system (IWRS) for randomization and also collected in the database by electronic case report form (eCRF) or central laboratory. The analysis models will use the stratification factors as collected in the database.

For the primary analysis of HbA1c, the stratification factor of HbA1c stratum will not be included. Instead, the continuous value of baseline HbA1c will be included in the analysis models.

Other efficacy analyses will include the stratification factors as noted in Sections 5.11 and 5.12.

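### The PedsQL ANCOVA lists a country term that has one level in a US-only addendum and omits age group, a randomization stratum; the cost is modest precision, not validity

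*SAP*

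**What the plan says.** SAP 5.11.6 gives the PedsQL model as an "ANCOVA model using treatment, strata (pooled country, type of basal insulin, and HbA1c stratum) as fixed effects and baseline score as a covariate". On who takes part, it says: "Patients and caregivers who are enrolled at sites in the US and who speak English will be asked to participate". It then fixes the analysis set: "The PedsQL Population will be used for all analyses specified in this section". No patient from outside the US therefore enters the model.

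SAP 5.2 begins its list with "Stratification factors of this study include country, HbA1c stratum" and goes on to type of basal insulin and age group (1 to <12, 12 to <18 years). For models other than the primary one it defers to later text: "Other efficacy analyses will include the stratification factors as noted in Sections 5.11 and 5.12".

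Protocol 10.3.1 sets out a general ANCOVA for continuous variables. The Week 26 HbA1c model "will include treatment and strata (pooled country, type of basal insulin, and age group) as fixed effects and baseline as a covariate". The section then adds a term for other outcomes: "For analyses of variables other than HbA1c, the HbA1c stratum" also enters the model. Nothing there says that this term takes the place of age group.

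**The concern.** Two things look wrong in one list of covariates. The model names an adjustment that cannot adjust for anything, because every patient in it comes from one country. It also leaves out a factor on which the trial balanced the arms.

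When randomization is stratified by a factor related to the outcome and the analysis ignores that factor, its variance stays in the residual. The reported standard error is then larger than it need be. Age may well matter for quality-of-life scores across 1 to <18 years: Protocol 3.1 notes that young children cannot always verbalize symptoms and that parental fear of hypoglycemia affects quality of life. What is at stake is some precision in an addendum outcome.

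**Working it through.** The plan states no sample size, power or variance for PedsQL, so there is no figure to reproduce. The check has three parts.

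**1. Does the country term do anything?** Count the columns of the design matrix for an all-US sample: intercept 1, treatment 2 (three arms), basal insulin 2 (three types), HbA1c stratum 1, baseline score 1. The total is 7, with rank 7. Adding country adds a constant column: 8 columns, rank still 7. No estimate, standard error or p-value changes. The pooling rule in SAP 5.1 and 5.4 merges small countries; it cannot split one country into levels. Adding age group instead gives 8 columns and rank 8, so that term can be estimated.

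**2. Which models carry age group?**

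| Model | Country | Basal insulin | HbA1c stratum | Age group |
|---|---|---|---|---|
| Protocol 10.3.1 ANCOVA, variables other than HbA1c | yes | yes | yes | yes |
| SAP 5.11.5 insulin dose and SMBG | yes | yes | yes | yes |
| SAP Appendix 2.4 CGM ANCOVA | no | yes | yes | yes |
| SAP Table ITSB.5.4 hypoglycemia (negative binomial and logistic models) | no | no | no | yes |
| SAP 5.11.5 HbA1c targets | no | no | no | no |
| SAP 5.12.5 laboratory, 5.12.6 vital signs | no | no | no | no |
| **SAP 5.11.6 PedsQL** | **yes (one level)** | **yes** | **yes** | **no** |

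The PedsQL model is the only one in this table that keeps the other three strata and drops age group.

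**3. What does the omission cost?** Let g be the difference between age groups, in residual SD units, that remains after baseline adjustment, and p the share of patients in one age group. The reported standard error without age group, relative to that with it, is about sqrt(1 + p(1 − p)g²). At p = 1/2, where this is largest, it becomes sqrt(1 + g²/4):

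- g = 0.2: sqrt(1.01) = 1.005
- g = 0.5: sqrt(1.0625) = 1.031
- g = 0.8: sqrt(1.16) = 1.077

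A simulation gave the figures below. Its assumptions, none of them from the documents except the 2:2:1 ratio, were 150 patients, half in each age group, permuted blocks of 5 within age strata, 4000 runs per setting and no true treatment effect.

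| g | SE ratio, without / with age group | Type I error without | Type I error with |
|---|---|---|---|
| 0 | 1.000 | 5.4% | 5.3% |
| 0.2 | 1.005 | 5.1% | 5.3% |
| 0.5 | 1.03 | 4.3% | 5.1% |
| 0.8 | 1.08 | 3.4% | 4.9% |

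The Monte Carlo error on a 5% rate is sqrt(0.05 × 0.95/4000) = 0.34 percentage points, so 5.4% does not differ from nominal. The mean estimated treatment difference was within 0.005 SD of zero throughout. At g = 0.8 the estimate varied by the same amount either way (empirical SD 0.1851 without age group, 0.1848 with it). Stratified randomization has already secured the precision; the model without age group fails to report it.

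**The case against.** The case for leaving the model alone has real substance.

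- **No rule is broken.** SAP 5.2 defers the choice of strata to 5.11 and 5.12, and 5.11.6 makes that choice. Protocol 10.3.1 lets the SAP describe changes of method that do not touch a principal feature. It also asks for a justification, and the SAP gives none for dropping age group. A reader might infer a breach of 5.2; the text does not support that.
- **Age group is not in every other model.** The laboratory, vital-sign, antibody and HbA1c-target models omit it too. A reader might infer that PedsQL is the lone exception; it is not.
- **Baseline score already does part of the work.** It takes up part of any stable difference between age groups, so g could be near zero.
- **Imbalance is limited by design.** Randomization is stratified by country and age group together, so large age imbalance among randomized US patients is unlikely. The PedsQL Population also depends on addendum consent and a completed post-baseline questionnaire, so exact balance within it is not guaranteed. That falls well short of showing bias.
- **The outcome carries little weight.** PedsQL is not among the twelve objectives, and SAP 5.5 makes no multiplicity adjustment beyond the primary and gated tests.

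These points limit the size and severity of the concern. None gives a reason to keep a constant term and leave out a stratum that is available.

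**Conclusion.** The point holds as a minor one. Pooled country is inert in this analysis, provided all US sites carry one country code, and age group is absent without explanation. The cost is a reported standard error about 0% to 8% too large for g between 0 and 0.8 SD, with a conservative test. The top of that range needs a large age effect: at g = 0.8, age group would explain 0.16/1.16 = 13.8% of the variance left after baseline.

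A stronger reading would be that the PedsQL comparison is biased or prone to false positives. The calculation points the other way: the estimate is essentially unbiased and the error rate is at or below nominal. Nor can one say that the loss is sharpened by a small subset, since the documents do not give the subset's size. Nothing here touches the primary or gated HbA1c analyses.

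**What to change.** In SAP 5.11.6, replace the pooled country term with age group (1 to <12, 12 to <18 years). The model then has treatment, type of basal insulin, HbA1c stratum and age group as fixed effects, with baseline score as covariate. These are the terms of the CGM ANCOVA in SAP Appendix 2.4.

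The cost is one phrase in the SAP and one degree of freedom. The PedsQL addendum is not among the documents available, so check first that it does not itself prescribe the model; if it does, amend or cross-refer to it. Make the change before unblinding, so that the covariates are not chosen with results in view.

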5.11.7. Analyses of Exploratory Objectives

The following endpoint derived from the 7-point SMBG profiles at each scheduled visit, will be analyzed using the MMRM model similar to that for the primary outcome with an additional term of HbA1c stratum ($\leq 8.0\%$, $>8.0\%$):

- 1-hour post-meal excursion
- between-day coefficient of variation (CV) and SD
- Within-day CV and SD

The excursion of SMBG will be calculated for each meal category (morning meal, midday meal, evening meal and all meals). The average value of excursions from the same visit for each patient will be used in the analysis.

Blood glucose (BG) values that are out of the detectable range (BG <20 mg/dL [1.1 mmol/L] or BG >600 mg/dL [33.3 mmol/L]) of the glucometer will be excluded from the analysis data. For baseline SMBG, records that are collected on or after the first dose date will be excluded from the analysis. If there are multiple records on the same day and same Timepoint, only the last entry will be used for variable derivation. BG readings without units will not be used in the analysis.

At a given visit, the CV and SD on each day with the 7-point SMBG profile will be calculated using all the glucose values within that day, then the average values of these CVs and SDs will be used as the within-day CV and SD at that visit in analysis. At a given visit, the CV and SD at each of the 7 pre-specified SMBG time points will be calculated using the corresponding glucose values of the 7-point SMBG profiles, then the average values of these CVs and SDs will be used as the between-day CV and SD at that visit in analysis.

5.12. Safety Analyses

Safety measures will include AEs, hypoglycemia, vital signs and weight, treatment exposure, laboratory measures, and antibodies to Humalog.

5.12.1. Extent of Exposure

Duration of exposure to study drug will be summarized. The following summary statistics will be provided: n, mean, SD, median, minimum, maximum, and sum (ie, total patient-years of exposure). The number and proportion of patients falling into the following different exposure categories will also be summarized: <1 month (>0 and <30 days), ≥1 and <3 months (≥30 and <90 days), ≥3 and <6 months (≥90 days and <180 days), and ≥6 months (≥180 days).

Patients who discontinue the IP prematurely are encouraged to remain in the study without study drug. The days on study after discontinuing IP, and the days on study from date of first study drug to the last study visit date up to Visit 801 will also be summarized.

5.12.2. Adverse Events

Analyses of AEs will include 2 sets of analyses, unless otherwise specified. The first set of analyses will include data collected prior to permanent discontinuation of IP. The second set of analyses will include all data collected during the course of the entire study including the follow-up visit, regardless of IP use.

Events that are newly reported after the first dose of IP or reported to worsen in severity from baseline will be considered treatment-emergent adverse events (TEAEs). The MedDRA Lowest Level Term (LLT) will be used in the treatment-emergent assessment. The maximum severity for each LLT during the baseline period will be used as baseline severity. For events occurring on the day of first dose of IP, the eCRF-collected flag will be used to determine whether the event started or worsened posttreatment.

In an overview table, the number and percentage of patients who experienced a TEAE, experienced serious adverse event (SAE), died due to an AE, discontinued from study due to an AE, or discontinued IP due to an AE will be summarized by treatment.

The number and percentage of patients with TEAEs will be summarized by treatment using MedDRA PT nested within System Organ Class (SOC). Events will be ordered by decreasing frequency within SOC. As an additional table, the percentages of patients with TEAEs will be summarized by treatment using MedDRA PT (without regard to SOC). Events will be ordered by decreasing frequency. Statistical comparisons will be applied at both the SOC and PT levels. Fisher's exact test will be performed for treatment comparison.

The number and percentage of patients with TEAEs by maximum severity will be summarized by treatment using MedDRA PT (regardless of SOC) and data collected prior to permanent discontinuation of IP. For each patient and TEAE, the maximum severity for the MedDRA PT is the maximum postbaseline severity observed from all associated LLTs mapping to the MedDRA PT. No statistical comparison between treatment groups will be conducted.

The number and percentage of patients with common TEAEs (defined as $\geq 5\%$ before rounding for LY900014 treated patients) will be summarized by treatment group using MedDRA PT (without regard to SOC). Events will be ordered by decreasing frequency. Treatment will be compared by Fisher's exact test.

The number and percentage of patients who experienced a SAE including deaths and SAEs temporally associated or preceding deaths will be summarized by treatment group using MedDRA PT regardless of SOC. Events will be ordered by decreasing frequency. A listing of all SAEs will also be provided.

The number and percentage of patients who discontinued from study due to an AE will be summarized by treatment group using MedDRA (without regard to SOC). The number and percentage of patients who discontinued IP due to an AE will be also summarized by treatment group using MedDRA PT (without regard to SOC). Events will be ordered by decreasing frequency. A listing of all AEs as reason for study or IP discontinuation will also be provided.

The number and percentage of patients who experienced other notable TEAEs (potential systemic hypersensitivity reaction, injection site reaction, and hepatic disorder) will be summarized by treatment group using all TEAEs regardless of IP use.

For events that are gender specific (as defined by MedDRA), the denominator and computation of the percentage will include only patients from the given gender.

For TEAEs occurring in $\geq 1\%$ of patients, a Kaplan-Meier plot of time to onset of the TEAE will be presented.

[Table ITSB.5.3](#) summarizes the planned analyses and the requirement of analysis data for different analysis periods. A "Yes" in the IP USE column indicates that only data collected prior to permanent discontinuation of IP will be included.

Table ITSB.5.3. Treatment-Emergent Adverse Event Analysis Periods

Analysis Period	Analysis Population	Analysis	IP USE	Treatment
Treatment Period (0-26 Weeks)	All patients in safety population	AE overview; TEAE by SOC and by PT; common TEAE; TEAEs by maximum severity; SAE; IP discontinuation due to AE; severe hypoglycemic events	Yes	LY900014, LY900014 +20, Humalog
Week 0 – Visit 801	All patients in safety population	AE overview; TEAE by SOC and by PT; common TEAE; SAE; other notable AEs (excluding severe hypoglycemic events); study discontinuation due to AE	All data regardless of IP use	LY900014, LY900014 +20, Humalog

Abbreviations: AE = adverse event; IP = investigational product; PT = Preferred Term; SAE = serious adverse event; SOC = System Organ Class; TEAE = treatment-emergent adverse event.

5.12.3. Deaths

The listing of all deaths by patient for all enrolled patients will be provided as part of the SAE listing, regardless of the investigator's or the sponsor's judgment about causality. Each listing will include study identification (ID), investigator ID, patient ID, treatment group, baseline age, sex, associated AE, first and last dose date for open label Humalog and randomized IP, and the event date.

5.12.4. Hypoglycemic Events and Other Adverse Events

The analysis plans for the following AEs are discussed in Section 5.12.4.1 through Section 5.12.4.4:

- hypoglycemic events
- systemic hypersensitivity reaction
- injection site reaction
- hepatobiliary events

5.12.4.1. Hypoglycemic Events

Hypoglycemia events that occur during the study will be captured in eCRF. Whenever hypoglycemia is suspected, the patient should record the BG value, any associated symptoms, and the treatment administered in patient diary.

A set of events will be considered as 1 event in analysis if the duration between adjacent events is within a 30 minute time window. The event with the highest severity will be selected for analysis with severity determined in the order of: 1) it is a severe hypoglycemia, 2) it has symptoms of hypoglycemia reported, and 3) it has the lowest blood glucose value. If there are multiple events tied in all 3 aspects, the event with the largest number of non-missing responses

to the questions of nocturnal hypoglycemia and post-dose time frame will be selected. If there are still multiple events tied, the latest event will be selected.

The following types of hypoglycemia events will be analyzed: documented hypoglycemia (with $BG \leq 70$ mg/dL [3.9 mmol/L] or $BG < 54$ mg/dL [3.0 mmol/L]), severe hypoglycemia, nocturnal hypoglycemia, and non-nocturnal hypoglycemia (with $BG \leq 70$ mg/dL [3.9 mmol/L] or $BG < 54$ mg/dL [3.0 mmol/L]). Only severe hypoglycemia will be collected as an AE and all episodes of severe hypoglycemia will be considered as SAEs.

Table ITSB.5.4 provides detailed statistical methods for each endpoint related to hypoglycemia. For these analyses, hypoglycemia events prior to the discontinuation of IP will be summarized. Additional analyses for other types of hypoglycemic events not mentioned in the table and for the posttreatment period may be conducted as needed.

A listing of patients with at least 1 severe hypoglycemia reported (as SAE) after randomization will be provided. A list of MedDRA PTs will be used for the narrow search of potential severe hypoglycemia in spontaneously reported AEs. The events identified through the search strategy that are also reported as SAEs will be summarized and compared between treatments. Fisher's exact test will be used to assess the treatment difference in the proportion of patients with potential severe hypoglycemia.

Table ITSB.5.4. Summary of Analyses for Endpoints Related to Hypoglycemia

Endpoint	Analysis Period	Statistical Method
Rate of hypoglycemic events (per patient per year) All Documented ^a Nocturnal ^a Non-Nocturnal (Documented and occurred between waking and bedtime) ^a	0-12, 0-26weeks	Negative binomial regression with treatment and age group as covariates, log (exposure/365.25 days) as the offset in the model.
Incidence of hypoglycemic events All Documented ^a Nocturnal ^a Non-Nocturnal (Documented and occurred between waking and bedtime) ^a	0-12, 0-26weeks	Logistic regression with treatment and age group as covariates.
Rate of post-dose hypoglycemic events (per patient per year) for all 3 main meals All Documented ^a	≤1, ≤2, ≤4, >4, and >2 to ≤4 hours after start of prandial insulin dose within 0-12, 0-26,weeks	Negative binomial regression with treatment and age group as covariates, log (exposure/365.25 days) as the offset in the model.
Incidence of post-dose hypoglycemic events for all 3 main meals All Documented ^a	≤1, ≤2, ≤4, >4, and >2 to ≤4 hours after start of prandial dose within 0-12, 0-26,weeks	Logistic regression with treatment and age group as covariates.
Rate of severe hypoglycemic events (per patient per 100 years)	0-12, 0-26weeks	Exposure adjusted rate 100 years (calculated by total number of events divided by total exposure for individual patients) will be provided and the empirical method (see Appendix 1 for details) will be used for treatment comparison.
Incidence of severe hypoglycemic events	0-12, 0-26weeks	Proportion of patients with severe hypoglycemia will be reported. The treatment comparison will be based on a logistic regression model with treatment and age group as covariates.

^a All documented hypoglycemia and the subcategories based on the thresholds of blood glucose ≤70 mg/dL and blood glucose <54 mg/dL will be analyzed.

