## 9.4. Safety

### 9.4.1. Hypoglycemia

Patients are encouraged to perform SMBG whenever hypoglycemia may be suspected, either by symptoms experienced or perceived increased risk as related to dietary intake, physical activity, or inadvertent or atypical insulin dosing. All patients will be instructed to treat a BG level  $\leq 70$  mg/dL (3.9 mmol/L) as hypoglycemia.

If a hypoglycemia event is suspected, patients should measure the BG value using the study provided meter and record the BG value in the diary, any associated symptoms, and the treatment administered in the study diary. The patient should contact the site as necessary. All hypoglycemia events (severe and non-severe) must be reported on the hypoglycemia electronic case report form (eCRF); see below and Section 9.4.2. All episodes of severe hypoglycemia must be reported as SAEs on the AE eCRF page and on the SAE eCRF page. Reports of hypoglycemia will be classified by the investigator as “severe” or “not severe” based upon data collected in the patient diary and in consultation with the patient. Episodes of hypoglycemia not meeting the criteria for severe hypoglycemia should not be reported as an AE.

Hypoglycemia will be described using the following definitions:

- **Documented Glucose Alert; BG $\leq 70$  mg/dL (3.9 mmol/L):**
  - **Documented symptomatic hypoglycemia:** an event with typical symptoms of hypoglycemia.
  - **Documented asymptomatic hypoglycemia:** an event without typical symptoms of hypoglycemia.
  - **Documented unspecified hypoglycemia:** with no information about symptoms of hypoglycemia available (this has also been called unclassifiable hypoglycemia).
- **Documented Clinically Significant Hypoglycemia with similar criteria as above, except for threshold BG $< 54$  mg/dL (3.0 mmol/L)**
  - **Documented symptomatic hypoglycemia**
  - **Documented asymptomatic hypoglycemia**
  - **Documented unspecified hypoglycemia**

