- **Severe Hypoglycemia:** during these episodes, patients have an altered mental status and cannot assist in their own care, may be semiconscious or unconscious, or experience coma with or without seizures, and require assistance of another person to actively administer carbohydrate, glucagon, or other resuscitative actions. Blood glucose measurements may not be available during such an event, but neurological recovery attributable to the restoration of BG concentration to normal is considered sufficient evidence that the event was induced by a low BG concentration (BG $\leq 70$  mg/dL [3.9 mmol/L]).
  - **Note:** Young children will frequently require assistance with treatment of hypoglycemia but are not experiencing signs of altered mental status or cognitive impairment. Final determination should be made by the investigator and based on a severe hypoglycemia event meeting the description provided above.
- **Other Hypoglycemia:**

- **Nocturnal hypoglycemia:** any documented hypoglycemic event (including severe hypoglycemia) that occurs between bedtime and waking.
- **Probable symptomatic hypoglycemia:** an event during which symptoms are present, but BG measurement was not reported.
- **Overall (or total) hypoglycemia:** this category combines all cases of hypoglycemia (documented hypoglycemia and probable symptomatic hypoglycemia, including severe hypoglycemia) excluding the events of relative hypoglycemia. Nocturnal and severe hypoglycemia are special cases of documented or probable hypoglycemia. If an event of hypoglycemia falls into multiple subcategories, the event is only counted once in this category.

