4. To compare LY900014, LY900014 +20, and Humalog with respect to the incidence and rate of documented post-dose hypoglycemia	4. Rate (events/patient/year) and incidence (percent of patients with events) of documented post-dose hypoglycemic events within 1 and 2 hours after the prandial dose from Week 0 through Week 26
5. To compare LY900014, LY900014 +20, and Humalog with respect to the incidence and rate of documented hypoglycemia	5. Rate (events/patient/year) and incidence (percent of patients with events) of documented hypoglycemic events from Week 0 through Week 26
6. To compare LY900014, LY900014 +20, and Humalog on the rate of severe hypoglycemic events	6. Rate (events/patient/100 years) of severe hypoglycemic events from Week 0 through Week 26

Objectives and Endpoints

Objectives	Endpoints
7. To compare LY900014, LY900014 +20, and Humalog with respect to total, basal, and prandial insulin dose	7. Change from baseline in total, basal, and prandial insulin doses and prandial/total insulin dose ratios at Week 26
8. To compare LY900014, LY900014 +20, and Humalog with respect to the proportion of patients achieving HbA1c targets	8. The proportion of patients with HbA1c <7% and <7.5% at Week 26
9. To compare LY900014, LY900014+20, and Humalog with respect to 7-point SMBG	9. Change from baseline to Week 26 in 7-point SMBG values
Tertiary/Exploratory Objectives	
10. To compare LY900014, LY900014 +20, and Humalog with respect to changes in body weight	10. Change in weight (kg) from baseline to Week 26
11. To compare LY900014, LY900014 +20, and Humalog with respect to glycemic variability	11. Within-day and between-day glycemic variability measured by the standard deviation and the coefficient of variation of 7-point SMBG profiles
12. To compare the incidence of treatment-emergent positive anti-insulin lispro antibodies for LY900014, LY900014 +20, and insulin lispro	12. Incidence of treatment-emergent positive anti-insulin lispro antibodies

Abbreviations: HbA1c = hemoglobin A1c; NIM = noninferiority margin; SMBG = self-monitored blood glucose; T1D = type 1 diabetes.

5. A Priori Statistical Methods

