5.5. Multiple Comparisons/Multiplicity

The test for superiority in HbA1c change from baseline (the second gated objective) will be conducted only when the test for noninferiority (the first gated objective) has been achieved. The gated objectives won't be conducted if the primary objective cannot be met.

No multiplicity test adjustment will be made for other objectives.

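### The 30-minute merging rule ranks severe status and symptoms above lowest glucose, so some sets containing a reading below 54 mg/dL are not counted below 54 mg/dL

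*SAP*

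**What the plan says.** SAP 5.12.4.1 treats adjacent events within 30 minutes as one event and selects a single record to stand for the set. The order is "1) it is a severe hypoglycemia, 2) it has symptoms of hypoglycemia reported, and 3) it has the lowest blood glucose value". It is sequential: only records tied on all three go to a further tie-breaker, where the record with the most complete responses "to the questions of nocturnal hypoglycemia and post-dose time frame will be selected". Nocturnal status and post-dose time are therefore attributes of individual records.

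Table ITSB.5.4 then analyses rates and incidence of documented, nocturnal, non-nocturnal and post-dose events. Footnote a applies two cut-offs, at or below 70 mg/dL and below 54 mg/dL: "All documented hypoglycemia and the subcategories based on the thresholds of blood glucose". These analyses serve secondary Objectives 4 and 5. The Objective 4 endpoint in SAP Table ITSB.4.1 covers "documented post-dose hypoglycemic events within 1 and 2 hours after the prandial dose".

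Protocol 9.4.1 defines the lower category by glucose: "Documented Clinically Significant Hypoglycemia with similar criteria as above, except for threshold" below 54 mg/dL. It has symptomatic, asymptomatic and unspecified subtypes, the asymptomatic one being "an event without typical symptoms of hypoglycemia". Symptoms do not decide membership. Section 9.4.1 also notes that a severe event may have no glucose measurement, and it defines probable symptomatic hypoglycemia as "an event during which symptoms are present, but BG measurement was not reported".

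**The concern.** The selection rule uses glucose last, but the analyses it feeds classify the selected record by glucose. Where a set mixes a reading below 54 mg/dL with a higher-ranked record that is not below 54, the reading that defines the category is discarded. Neither document says that the lowest value is kept with the selected record, or that selection is repeated for each threshold.

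At stake is the count in the category the protocol calls clinically significant, in a trial that enrols from age 1. Protocol 3.1 says that young children may be unable to verbalize symptoms, so low readings without reported symptoms are to be expected. Protocol 9.1.5.1 asks patients to test when hypoglycemia is suspected, with or without symptoms, so closely spaced records are plausible.

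**Working it through.** The plan states no figure to reproduce. The check applies the rule to every relevant two-record set.

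**Inputs.** The window and order come from SAP 5.12.4.1, the two thresholds from Table ITSB.5.4 footnote a, and category membership by glucose from Protocol 9.4.1. Each set holds one non-severe record at 50 mg/dL, with or without symptoms, and one companion. Severe records are taken as symptomatic. Illustrative values are 50 for below 54 and 66 for 54-70 mg/dL.

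**Results.** *SAP rule* is the order as written. *Lowest glucose* represents the set by its lowest-glucose record.

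| Companion record | Combinations | Lost below 54, SAP rule | Lost at or below 70, SAP rule | Lost below 54, lowest glucose |
|---|---|---|---|---|
| Non-severe, 66 mg/dL, symptoms yes/no | 4 | 1 | 0 | 0 |
| Severe, 66 mg/dL | 2 | 2 | 0 | 0 |
| Severe, no glucose | 2 | 2 | see below | 0 |
| Total | 8 | 5 | | 0 |

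The order of the two records in time does not change any result. These are counts of logical patterns, not frequencies. Of the 5 losses, 4 involve a severe companion.

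- The single non-severe loss is the 50 without symptoms beside the symptomatic 66.
- For a severe record without glucose, the count at or below 70 mg/dL depends on how the recovery clause in Protocol 9.4.1 is applied. On recorded glucose alone, that count is lost too.
- The SAP does not say whether probable symptomatic records, which have no glucose, enter the merge. If they do, 1 of 2 combinations is lost from both thresholds.
- A record below 54 that stands alone, or merges only with non-severe records without reported symptoms, is still counted. Two records below 54 (53 symptomatic, 40 asymptomatic) still give one event below 54.

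**Timed examples.**

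1. Symptomatic 66 at 50 minutes post-dose and asymptomatic 50 at 70 minutes. The SAP rule selects the 66 and counts no event below 54. Lowest glucose selects the 50 and counts one event under each threshold at 70 minutes: within 2 hours, not within 1 hour.
2. Symptomatic 66 at 115 minutes and asymptomatic 50 at 125 minutes. If selection were run separately for each threshold, the analysis at or below 70 would take 115 minutes and the analysis below 54 would take 125 minutes. In the >2 to ≤4 hour window this gives one event below 54 and none at or below 70. Lowest glucose places both at 125 minutes, so nesting holds.
3. Three-record chain: asymptomatic 50 at 50 minutes, symptomatic 62 at 75, asymptomatic 68 at 100. The SAP rule selects the 62 and counts none below 54. Lowest glucose counts one, at 50 minutes.

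**Scale, on assumed inputs only.** For a non-severe pair with one reading below 54 and one at 54-70, and symptoms independent, the share lost is P(symptoms | 54-70) × [1 − P(symptoms | <54)]. With assumed probabilities of 0.3 to 0.7 and 0.5 to 0.9, it runs from 0.3 × 0.1 = 3% to 0.7 × 0.5 = 35% of such mixed pairs. How common such pairs are is unknown. If a share f of all sets with a reading below 54 is lost, the rate is multiplied by 1 − f: an assumed f of 0.1% to 5% gives 0.999 to 0.95. The rate ratio is multiplied by (1 − f₁)/(1 − f₀), which is 1 when f is the same in both arms.

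**The case against.** The strongest reply is that this is a complete, prespecified rule applied identically to all arms. Any rule keeping one record per episode gives up some attribute, and putting clinical severity and symptoms ahead of a number is defensible. The protocol says nothing about merging, so no protocol rule is broken. The main non-severe pattern needs two separately reported events within 30 minutes, the lower without symptoms and the higher with them. Sets with a severe companion remain in the severe analyses, the serious adverse event listing and the narratives. Objectives 4 and 5 do not name the 54 mg/dL cut-off, and SAP 5.5 says of objectives outside the gated sequence: "No multiplicity test adjustment will be made for other objectives".

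Most of this stands, and it limits the point to a modest one. It does not remove it. A rule may choose a representative record on clinical grounds, but the SAP then classifies that record by glucose and does not acknowledge the loss. Table ITSB.5.4 reports no symptom subcategories, so nothing in it needs the symptom ranking.

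A reader might infer three stronger things.

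- *The comparison between arms is biased.* The documents give no reason to expect mixed sets to be more common in one arm, and an equal proportionate loss cancels in the rate ratio.
- *All documented hypoglycemia is undercounted.* With glucose recorded on both records, the count at or below 70 mg/dL is intact. It is at risk only in the conditional cases without glucose.
- *The SAP contradicts the protocol.* Protocol 9.4.1 defines categories for an event and does not say how several reports become one. The mismatch is between the glucose basis of the category and the way the SAP fills it.

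**Conclusion.** The point holds. Followed as written, the rule removes some qualifying sets from the category below 54 mg/dL and never adds any, so the error is a one-way undercount in the documented, nocturnal, non-nocturnal and post-dose analyses. Patient-level incidence changes only when the lost set was that patient's only event below 54 mg/dL in the analysis period. The size cannot be derived from the documents and is probably small. The severe count and the HbA1c objectives are unaffected.

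This rests on reading the selection order literally and on there being no unstated step that filters records by threshold before merging. If such a step is intended, the SAP should say so. The point is worth fixing because the category is a safety measure and the correction is cheap; it is not a threat to the trial's main conclusions.

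**What to change.** Keep the 30-minute sets and the severe-hypoglycemia count as they are. For the glucose-threshold analyses of Table ITSB.5.4, represent each set by its lowest-glucose record among records that have a glucose value, with the existing order as tie-breaker. Use that same record, with its own nocturnal and post-dose-time responses, for both thresholds. Events below 54 mg/dL then stay nested within events at or below 70 mg/dL in every window, and no set combines the glucose of one record with the timing of another. Also state whether records without glucose enter the merge, and how a set with no glucose value at all is classified.

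The cost is one or two SAP sentences and a small programming change, with no new data. Rates below 54 mg/dL may rise slightly. Some events at or below 70 mg/dL may move to a different post-dose or nocturnal window, as in the first timed example, where the event leaves the 1-hour window.

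If selection is instead run separately for each threshold, the SAP should state that events below 54 mg/dL may then not be nested within events at or below 70 mg/dL inside a time window.
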